Aims and Objectives	
Aim
 
To evaluate the effectiveness and cost-effectiveness of a clinical guideline implementation strategy (CLECC-Pal Delirium) to improve the early detection, management and prevention of delirium among palliative care unit (PCU) in-patients.
 
Primary objective
 
To evaluate the effectiveness of the CLECC-Pal Delirium intervention compared to usual practice to reduce the proportion of inpatient days affected by delirium in PCUs in a fully powered cRCT.
 
Secondary objectives (process related outcomes and clinical outcomes):
 
 1. To identify adherence to delirium care guidelines (for the detection, assessment, management, and prevention of delirium) at baseline and follow up 2. To explore symptom burden and functional status during inpatient admissions, and their relationship with days affected and not affected by delirium. 3. To evaluate the cost-effectiveness of CLECC-Pal Delirium compared to usual practice on reducing the proportion of inpatient days affected by delirium in PCUs 4. To improve understanding of how CLECC-Pal-Delirium could be scaled-up across the UK
Study Design	
Adaptive implementation-to-target cluster randomised controlled trial with concurrent economic evaluation and process evaluation.
 
DAMPen-DII is broken down into 3 distinctive work packages (WP1, WP2 and WP3). WP1 involves the study set-up, obtaining regulatory approvals and engaging with Palliative Care Units who may want to participate in the study. WP2 involves the start of the cluster randomised controlled trial with an inbuilt

	
pilot study. WP2 also includes a process evaluation section (WP2c) and health economic evaluation (WP2b) to evaluate the effectiveness and cost-effectiveness of CLECC-Pal Delirium compared to usual practise.
 
WP3 aims to engage and inform stakeholders about study findings and explore how the CLECC-Pal Delirium implementation strategy could be adapted for use in other settings.

Number/Type of Participants	We will collate approximately 50 sequentially admitted inpatient records from each of the 20 PCU sites at 2 time points (approximately 1000 records at baseline and approximately 1000 records at follow up). Refer to Sample Size Rationale below.
Site PCU Eligibility	
Inclusion criteria
 
 1. Charitably-funded or NHS PCU providing specialist palliative care inpatient services 2. Willing to provide access to inpatient medical records 3. Capacity and capability to undertake intervention training. 
Exclusion criteria
 
 1. Sites without capacity to support the intervention
Inpatient Eligibility	
Inclusion criteria:
 
 1. Sequentially admitted inpatients to a site PCU who have not opted out 
Exclusion criteria:
 
 1. Any site PCU inpatient who has opted out of research (as documented either in the opt out register or medical records, or who has communicated to site staff that they do not want to take part) will be omitted from the consecutive inpatient list and data collection process.
Study Treatment(s)	Cluster RCT (cRCT) with site PCUs randomised (1:1) to the study intervention arm or the usual practice arm
End of Trial	Receipt and successful linkage of all HES data with the clinical record data, and completion of all patient/carer and staff interviews
Study Endpoints and Statistical Methods	
Primary outcome measures (clinical):
 
For inpatients who experience delirium during PCU admission, the proportion of inpatient days affected by delirium calculated as the number of days they experience delirium (as identified with Inouye tool by HHTU researchers) divided by their total number of inpatient days.

	
Secondary outcomes (process related and clinical):
 
1. Guideline adherence
 
Number of inpatient records that contain evidence of adherence to delirium care guidelines (for the detection, assessment, management and prevention of delirium) at baseline and follow up.
 
 • Use of 4AT screening tool • Presence/absence of delirium risk assessment • Use of Richmond Agitation-Sedation Scale-Pal • Clinician-documented diagnosis of delirium • Clinician assessment of cause/reversibility • Presence/absence of delirium care plan • Use of antipsychotics in relation to documented harmful/distressing behaviour towards self or others 
2. Cost-effectiveness
 
Incremental cost-effectiveness ratio quantifying the cost per PCU inpatient day affected by delirium which is avoided.
 
3. Inpatient Demographics
 
 • Age • Sex • Diagnosis • Ethnicity • Postcode (converted to IMD score at data collection) • Primary Medical Condition • Date Of Death (if applicable) • Length of stay

Sample Size Rationale
	
This complex sample size rationale is based on a combination of i) numbers at risk of delirium, ii) numbers who incur delirium episodes, and iii) length of these delirium episodes. It is informed by patient and public partners perspective that – in the context of advanced illness - every day without delirium is a real gain and highly valued. So based on delirium episodes in the previous feasibility study, we expect a minimum of 50 consecutive inpatient records will be required (from each site and at two timepoints) to identify 30 delirium episodes at baseline and 30 episodes at follow up (total 1200 delirium data records). We will collate data records from PCU inpatients (stopping record identification at each site as soon as 30 delirium episodes have been identified) at both timepoints (baseline and follow up) to obtain a total of 1200 episodes of delirium (600 baseline and 600 follow-up,) to achieve a 92.3% power required to detect a 12% reduction of proportion of inpatient days affected by delirium, at 0.05 significance level, assuming an ICC of 0.03. We expect reduced duration of delirium episodes in the follow up group after the interventions, so will review adequate consecutive inpatient records during the follow-up period to ensure the data collection of 30 delirium episodes per site

Schedule Of Events (Dampen-DII Study)

Schedule Of Events (WP 2)

Activity	-12 weeks	- 4 weeks	Baseline	Intervention Period ^C	Follow Up ^D	Dissemination period
cRCT (WP2a)						
Site PCU set-up/contracting ^A	X					
Site PCU cluster randomisation		X				
Poster display ^B		X				
Screening			X			
Research 'Opt out' checks			X			
List of Baseline 50 consecutive inpatients sent to researcher			X			
Baseline data collection at site PCU ^E			X	X	X	
Study CLECC-Pal Delirium intervention (inc. training delivery) ^F				X		
List of Follow Up 50 consecutive inpatients sent to researcher				X	X	
Follow up data collection at site PCU ^E					X	
NHS England data collection ^G			X	X	X	X
Process Evaluation (WP2c)						
PIS and approach					X	
Consent					X	
Interviews					X	

^A Including start-up facilitation with intervention sites (weekly phone/online call with clinical lead to discuss how common barriers for delirium guideline implementation can be addressed and core actions needed to achieve implementation-readiness)

^B Display for 4 weeks before starting collation of records of consecutive patients who completed their inpatient stay during the time period from display of poster to start of intervention^Cstudy intervention to start in the intervention arm PCUs only after the baseline list of 50 sequential inpatients has been sent to the researcher^DFollow up collation of consecutive patient records to start in order to capture patients who complete their inpatient stay from the beginning of the seventh calendar month after the PCU starts the intervention (in the intervention arm) or continues usual practice (in the control arm)^EEMR e.g. SystemOne or EMIS, or paper records^F Intervention to start only when implementation-readiness criteria are met (see section XX for more detail) ^GNHS England data collection can take place as soon as DARS application has been approved

1. Background & Rationale

People nearing the end of life have a high risk of delirium,^{1, 2, 3, 4} a neurocognitive condition of impaired awareness, attention, and cognition.⁵ Delirium is highly distressing for patients and families, increases health professionals' anxiety and stress,⁶ and leads to poor clinical outcomes and higher care costs.^{7, 8}

Delirium is a common occurrence, especially for those in-patient Palliative Care Units (PCUs), with the most advanced illness. One-third of people cared for by adult in-patient PCUs, such as hospices, have delirium on admission, with a further one-third developing delirium during their stay.⁴ In practice, delirium is often underestimated due to hypoactive delirium (where patients are quiet and withdrawn) not being recognised.⁹ About half of PCU in-patients are admitted for symptom management and discharged following optimised management, yet an episode of delirium carries a higher risk of subsequent cognitive decline, care home placement or repeat hospital admissions.¹⁰ Effective delirium care needs prevention, timely detection and non-pharmacological management, with pharmacological interventions if appropriate.^{11, 12} However, implementation of evidence-based guidelines^{13, 14} and standards¹⁵ to achieve this is poor. This leads to persistent poor practice such as routine use of antipsychotics to treat delirium¹⁶ despite evidence to the contrary.^{17, 18} In PCUs, the complex interactions between patients, family, and clinicians in diverse organisational and cultural contexts^{19, 20, 21} means that not just education but practical and emotional support for staff is required to implement evidence-based change.¹⁹

An eight-study systematic review of PCUs showed delirium prevalence varied from 13.3% to 42.3% at admission and 26% to 62% during admission,³ similar to our recent feasibility study findings (23% and 41%, respectively).²² A review of 42 studies across all palliative settings gave delirium point prevalence estimates of 4% to 12% (community), 9% to 57% (hospital palliative care consultative services), and 6% to 74% (palliative care in-patient units).⁴ A systematic review and meta-analysis (28 studies) of delirium risk factors in adults receiving specialist palliative care¹ found that although some were unmodifiable (type of cancer, older age and male sex), modifiable factors such as opioids, dehydration, hypoxaemia, and poor sleep were found, challenging views that 'nothing can be done' at this stage.

The impact of delirium and its psychological sequelae for patients, carers, and healthcare staff is under-acknowledged, despite the significance of the distress caused.^{23, 24} Delirium is associated with poor outcomes, including increased post-discharge mortality, functional decline, longer hospital stays²⁵ and higher healthcare costs,^{7, 26} new institutionalisation, and worsening dementia.^{27, 28} Poor outcomes may appear less important for people with shorter prognoses, but gaining better quality time at home without mental deterioration is extremely important for many. Delirium also jeopardises care in the community, and our Public Advisory Group have confirmed

how preserving mental capacity and communicating with loved ones is crucial for decision-making and reducing distress.

Non-pharmacological interventions reduce delirium risk²⁹ and are recommended in National Institute for Health & Care Excellence (NICE) and Scottish Intercollegiate Guidelines Network (SIGN) guidelines.^{13, 14} There is a limited role for medication.^{30, 31} Despite this, and the person-centred culture and good staff levels in palliative care units, guideline-adherent delirium care is poorly implemented,³² with action needed at patient, carer, clinician, team and system levels.^{19, 21, 33, 34} Validated delirium risk-assessment tools such as the 4AT³⁵ support delirium management, but have low rates of use in PCUs.³²

An information specialist search of databases (Medline, Embase, Psycinfo, CINAHL, CDSE, Epistemonikos, Caresearch) and registries (Europe PMC Grant finder, Clinical Trials.gov, UKCTG, Prospero, ISRCTN, WHO International Clinical Trials) conducted in August 2023 identified trials of multi-component delirium interventions (without implementation strategies) in hospital settings, with one pilot study in Australian PCUs.³⁶ Two quality improvement projects in PCUs^{37, 38} and feasibility studies in PCUs²⁰ and care homes³⁹ give valuable insights, but little further guideline implementation research has been done in these settings other than our completed feasibility work.²² In this completed study, we: i) tailored a staff educational and empowerment implementation strategy for use in PCUs (*CLECC-Pal Delirium*); ii) confirmed we can reliably collect data to assess both patient and implementation outcomes from patient records; iii) obtained data to calculate sample size for a national cluster randomised controlled trial; and iv) showed a signal of benefit (6% reduction in proportion of inpatient days affected by delirium, for those with a delirium episode). We have therefore demonstrated feasibility of the implementation strategy and trial, but now need to definitively test effectiveness in a powered trial.

About half a million people die in England each year, with a high proportion (42-88% across all settings) suffering delirium during last year of life,⁴ often contributing to unplanned hospital admissions that account for 47% (£346m/year) of all health and social care costs in the last year of life.⁴⁰ Delirium causes increased length of hospital stay, staff time, and higher levels of hospital-associated adverse events, leading to higher costs of care (e.g. £349 average cost per palliative care bed day)⁴¹ and additional suffering for patients. Although more evidence is needed, delirium interventions may be cost-effective by preventing and shortening delirium episodes, reducing falls, and improving functional ability.⁴² Unplanned hospital admissions are also reduced.⁴³ However, implementing evidence-based delirium guidelines remains a challenge.

Evidence-based guidelines support the use of multi-component delirium care to prevent and manage delirium,^{13, 14} but there is no evidence on how best to implement such care into routine practice and little rigorous evidence about the cost-effectiveness of

interventions to prevent and manage delirium.⁴² A recent Cochrane review of non-pharmacological approaches to preventing delirium outside of intensive care concluded that future research should focus on implementation and how intervention components should be tailored for different settings.²⁹

This study addresses James Lind Alliance research priority 17 in palliative care,⁴⁴ the NICE delirium research recommendations¹³ (updated January 2023) regarding assessment and staff education for improving clinical outcomes, and our Public Involvement Group members' strong emphasis on the importance of implementing delirium assessment, management, and prevention in PCUs.

We will test the effectiveness and cost-effectiveness of a co-designed implementation strategy (*CLECC-Pal Delirium*) in the high prevalence setting of PCUs and explore its transferability to other high prevalence settings where implementing change in delirium care is challenging (care homes³⁹) or has high impact (own home).⁴⁵

2. The Study Intervention - CLECC-Pal Delirium

All site PCUs will continue to follow standard clinical care management during this study. Site PCUs randomised to the CLECC-Pal Delirium intervention arm will in addition follow the study intervention components (collectively termed the CLECC-Pal Delirium implementation strategy). The five components of CLECC-Pal Delirium include a study training day, mid-shift cluster discussions, peer observations of practice, reflective discussions, and action learning sets. The CLECC-Pal Delirium intervention aims to create a secure learning environment that delivers new ways of working, supporting implementation of delirium management guidelines and is described in Table 1.

A wide range of site PCU staff e.g. healthcare assistants, nurses, allied health professionals (e.g. physiotherapist, OTs), therapy professionals (e.g. music therapists), doctors, volunteers, care managers and executive board members will be expected to take part in the components of CLECC-Pal Delirium as part of their day-to-day practice.

Table 1: The Five Components of the CLECC-Pal Delirium Intervention

Component	Why	What	Who, how, where	When / How much
Study Day	Delirium management and prevention skills, CLECC-Pal Delirium components and how to put into practice	Presentations, interactive, discussions and planning	On-site with all hospice staff, day coordinated and led by researcher	One day
Mid-shift cluster discussions	Opportunities for feedback, group problem solving, and support to individual team members	Delirium focussed review	Ward staff at specified times during shifts	5 minutes a day
Peer Observation of practice	Opportunity to learn from constructive feedback	Feedback on observations of practice	PCU Delirium Lead during shifts	Depending on activities observed, 5-60 minutes per observation and feedback (6-10 occasions)
Reflective discussions	To prompt personal reflections and narratives about individual experiences	Scheduled meetings or drop-in sessions with planned activities	All team members including senior staff and temporary staff, facilitated by clinical lead	Number and frequency determined by hospice need (at least once)
Action learning needs	Share practice challenges and devise action plans	Group action plan development to address identified problems	All team members, including senior staff and temporary staff, facilitated by clinical lead	Number and frequency determined by hospice need (at least once)

2.1. Presence or Absence Delirium (Inouye Tool)

Clinical record data will be extracted using an expanded version of the prospectively validated (74% sensitivity, 83% specificity) chart-based instrument developed by Inouye et al. for detecting potential delirium diagnoses from clinical records. The instrument (CRF) will enable us to assess whether case-note recorded symptoms of delirium can be linked to time-points during the person's admission when actions around delirium assessment, management and prevention (consistent with guidelines) did or did not take place ⁴⁸.

3. Aim And Objectives

3.1 Aim

To evaluate the effectiveness and cost-effectiveness of a clinical guideline implementation strategy (*CLECC-Pal Delirium*) to improve the early detection, management and prevention of delirium among palliative care unit (PCU) in-patients.

3.2 Primary Objective

To evaluate the effectiveness of the *CLECC-Pal Delirium* intervention compared to usual practice to reduce the proportion of inpatient days affected by delirium in PCUs in a fully powered cRCT.

3.3 Secondary Objectives (Process Related Outcomes And Clinical Outcomes):

1. To identify adherence to delirium care guidelines (for the detection, assessment, management, and prevention of delirium) at baseline and follow up
2. To explore symptom burden and functional status during inpatient admissions, and their relationship with days affected and not affected by delirium.
3. To evaluate the cost-effectiveness of *CLECC-Pal Delirium* compared to usual practice on reducing the proportion of inpatient days affected by delirium in PCUs
4. To improve understanding of how *CLECC-Pal-Delirium* could be scaled-up across the UK

3.4 Outcome measures

3.4.1 Primary Outcome Measure (Clinical)

For inpatients who experience delirium during PCU admission, the proportion of inpatient days affected by

delirium calculated as the number of days they experience delirium (as identified with Inouye tool by HHTU researchers) divided by their total number of inpatient days.

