3.4.2 Secondary Outcomes (Process-Related And Clinical)

i. Guideline adherence

Number of inpatient records that contain evidence of adherence to delirium care guidelines (for the detection, assessment, management and prevention of delirium) at baseline and follow up.

- Use of 4AT screening tool
- Presence/absence of delirium risk assessment
- Use of Richmond Agitation-Sedation Scale-Pal
- Clinician-documented diagnosis of delirium
- Clinician assessment of cause/reversibility
- Presence/absence of delirium care plan
- Use of antipsychotics in relation to documented harmful/distressing behaviour towards self or others

ii. Costs

Incremental cost-effectiveness ratio quantifying the cost per PCU inpatient day affected by delirium which is avoided.

iii. Inpatient Demographics

- Age
- Sex
- Diagnosis
- Ethnicity
- Postcode (converted to IMD score at data collection)
- Primary medical condition
- Date of death (if applicable)
- Length of stay

4. Study Design

The study will be conducted in 3 related parts - Cluster RCT (cRCT) interventional study (Adaptive 'implementation-to-target' cRCT) with site PCUs randomised to the CLECC-Pal Delirium intervention or usual practice, health economic evaluation, and a parallel process evaluation (refer to [6](#) and [7](#) respectively). Information about the internal pilot (study set up feasibility and timelines) and Knowledge Exchange workshops (engagement with stakeholders about actions for future practice and policy) is included in Appendix A and B, respectively.

5. Cluster randomised-controlled trial

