5.4 Sample size

Based on delirium episodes in the previous feasibility study, we expect a minimum of 50 consecutive inpatient records will be required (from each site and at two timepoints) to identify 30 delirium episodes at baseline and 30 episodes at follow up (total 1200 delirium data records). We will collate data records from PCU inpatients (stopping record identification at each site as soon as 30 delirium episodes have been identified) at both timepoints (baseline and follow up) from 20 sites to obtain a total of 1200 episodes of delirium (600 baseline and 600 follow-up) to achieve a 92.3% power required to detect a 12% reduction of proportion of inpatient days affected by Delirium, at 0.05 significance level, assuming an ICC of 0.03.

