6.2 Data Analysis

We will estimate incremental effectiveness of the intervention using the primary outcome (Site PCU inpatient days affected by delirium). We have chosen cost-effectiveness analysis over cost-utility analysis in the context of practical and ethical challenges in primary data collection of generic health related quality of life (HRQoL) data in our population and study design. In secondary analyses, we will explore relationships between IPOS and AKPS scores with delirium and non-delirium days at sites where these data are collected, and explore the scope for using these in cost-effectiveness analyses, thus investigating if incorporating a wider set of HRQoL domains affects our interpretation and conclusions.

Prior to conducting primary analysis, we will examine: (i) baseline differences on characteristics associated with outcome and where necessary control for baseline variables in analysis; and (ii) skew, kurtosis and heteroscedasticity in the cost data and fit an appropriate (most likely, nonlinear) model. We will address missing outcome data using multiple imputation. We will bootstrap each set of regressions with 1000 replications and combine these bootstrapped results in estimating cost-effectiveness acceptability curves. If data characteristics require it, we will account for correlated costs and effects using seemingly unrelated regressions. Recognising the uncertainty associated specifically with a cRCT, we will employ a stratified two-stage nonparametric bootstrap resampling procedure for clustered data. We will use discount rates in line with NICE guidance at the time of analysis. For the purposes of cost-effective analyses, each day affected by delirium will be treated as a 'whole (24 hour) day'.

Data analysis will include:

- Estimation of the cost of a day in PCU, stratified by PCU type, using personal social services research unit (PSSRU) data, differentiating between staffing costs for patients with and without delirium, based on staff logs and discussions with clinicians and managers.
- Estimation of associated hospital admission costs using reference costs adjusted for HRG code, co-occurring conditions including delirium, and length of stay. We will adjust for the additional cost associated with an acute hospital admission ending in death.
- Estimation of the resources associated with the CLECC-Pal Delirium study intervention through review of staff activity and discussions with clinicians and managers.

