7.2.3 Participant selection

The Site PI (or suitable delegated PCU staff member) will take informed consent from staff and inpatients/carers and contact details will be sent to the research team to secure HHTU study NHS email. After consenting inpatients/carers, PCU staff will promptly contact the HHTU team to schedule the HHTU researchers to come to the PCU to conduct the interviews of inpatients/carers. Interviews will be conducted with the inpatients/carers remotely, if preferred by participant.

When on site the HHTU researchers will review the completed consent forms for accuracy and completeness and will take the hard copies for secure storage at HHTU (ensuring copies remain at site).

The HHTU researchers will confirm with the PCU staff that no changes in capacity have occurred since consent was given prior to the interviews. When confirmed the PCU staff will help the HHTU researchers identify the correct PCU inpatients that have consented. For staff members that have consented to interview their details will be collected by the Site PI and emailed through to the HHTU research team. Consented staff members will be contacted remotely by the HHTU research team.

The research team will add the contact details and will upload the signed informed consent form to the secure web-based study database managed by HHTU.

Interviewees will be selected by the researcher to obtain maximum diversity of interviewees, that is, a range of type of staff roles and grades and a range of patients/families from different socio-economic backgrounds and ethnic groups.

Purposive sampling of inpatients will be undertaken to interview those who have experienced delirium and those who have not, as the intervention covers both prevention and management of delirium.

Not all those who have expressed an interest to be interviewed will be selected due to purposive sampling methodology.

Inpatients/Carers Inclusion Criteria:

- Inpatients with capacity to consent
- Carers of inpatients with capacity to consent

Inpatients/Carers Exclusion Criteria:

- Patients who do not have capacity at point of interview will be withdrawn
- Carers of inpatients without capacity to consent

Staff Inclusion Criteria

- PCU staff members with patient contact
- Member of PCU management or Executive

Staff Exclusion Criteria

-Staff without patient contact (not including managerial roles)

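### The primary outcome counts only inpatients who experience delirium, so delirium that is fully prevented earns no credit and the arms are compared on groups the intervention can change

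*Protocol*

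**What the plan says.** - **Primary outcome.** Section 3.4.1 sets it "For inpatients who experience delirium during PCU admission, the proportion of inpatient days affected by" delirium, that is, delirium days divided by total inpatient days. The Trial Summary and Table 2 use the same restriction.
- **Aim and objective.** Section 3.1 wants "to improve the early detection, management and prevention of delirium among palliative care unit (PCU) in-patients". Section 3.2 seeks "to reduce the proportion of inpatient days affected by delirium in PCUs in a fully powered cRCT", with no restriction to affected patients, and the objective as worded in Table 2 refers to the total proportion of inpatient days. Section 7.2.3 justifies interviewing patients with and without delirium "as the intervention covers both prevention and management of delirium".
- **Sampling.** Section 5.4 plans on "stopping record identification at each site as soon as 30 delirium episodes have been identified". The sample size rationale in the Trial Summary expects shorter episodes at follow-up, "so will review adequate consecutive inpatient records during the follow-up period to ensure the data collection of 30 delirium episodes per site".
- **Secondary analyses.** Section 5.9.3 adds time to first delirium, with death as a competing risk, and calls it a key secondary outcome. It also summarises the proportion with delirium for each unit by arm and timepoint. The outcome list in section 3.4.2 contains neither.
- **Economics.** Section 3.4.2 names an "Incremental cost-effectiveness ratio quantifying the cost per PCU inpatient day affected by delirium which is avoided". Section 6.2 says: "We will estimate incremental effectiveness of the intervention using the primary outcome (Site PCU inpatient days affected by delirium").

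**The concern.** Whether a patient has delirium is settled after the units are randomised, and the strategy is meant to alter it. Restricting the primary comparison to patients with delirium therefore selects on something the intervention can change. Randomisation makes the arms' inpatients comparable in expectation. It does not do so for the arms' delirium cases once some cases have been prevented.

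A fully prevented case also disappears from the comparison, and collecting records up to 30 episodes per site replaces it with another case. The same absolute benefit can then show as a gain, as nothing or as a loss, depending on which cases were prevented. The trial could report a neutral or adverse primary result for a strategy that reduced delirium across the unit, or a flattering one for the opposite reason. The economic evaluation takes its effect from the same outcome, so the ambiguity carries over.

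**Working it through.** **1. The plan's own power figure (section 5.9.1).** Inputs: 20 units randomised 1:1, 30 episodes per unit, 70% v 58%, effect size 0.4, ICC 0.03, alpha 0.05 (taken as two-sided).
- SD = 0.12 / 0.4 = 0.30
- Design effect = 1 + (30 − 1) × 0.03 = 1.87
- Effective n per arm = 300 / 1.87 = 160.4
- Noncentrality = 0.12 / (0.30 × √(2/160.4)) = 3.58; noncentral t with 18 df gives power 92.3%

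The stated 92.3% is reproduced. It is power for the outcome in patients with delirium.

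**2. What prevention alone does.** Section 1 gives 23% with delirium at admission and 41% during admission in the feasibility study. I read the 41% as including the 23%, so 18% are later cases. The 70% mean is from section 5.9.1. Its split between admission cases (mean a) and later cases (mean b) is not given, so I vary it subject to 0.23a + 0.18b = 0.41 × 0.70 = 0.287. Now prevent half of the later cases and change nothing else:
- All-inpatient burden = 0.23a + 0.09b (28.7% before)
- Primary outcome = (0.23a + 0.09b) / 0.32 (70% before)

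| a | b | All-inpatient burden after | Primary outcome after |
|---|---|---|---|
| 60% | 82.8% | 21.25% | 66.4% |
| 70% | 70.0% | 22.4% | 70.0% |
| 80% | 57.2% | 23.55% | 73.6% |
| 90% | 44.4% | 24.7% | 77.2% |

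Burden falls by 4 to 7.5 points in every row. The primary outcome falls by 3.6 points, stays put, or rises by up to 7.2 points, against a target of 12.

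If the 41% instead excludes the 23% (64% in all), the constraint is 0.23a + 0.41b = 0.448 and the primary outcome after prevention is (0.23a + 0.205b) / 0.435. For a = 60% this gives 67.4%, and for a = 90% it gives 75.3%. The pattern is the same.

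**3. Power of an all-inpatient measure (delirium-free stays scored 0).** Assumptions: 50 records per unit, ICC 0.03, SD 0.30 among cases, the full 12-point effect in cases, no prevention, and delirium risk p of 41% (feasibility) to 60% (30 episodes per 50 records, treated as patients).
- Variance in an arm with case mean μ = p(0.09 + μ²) − (pμ)²
- Design effect = 1 + 49 × 0.03 = 2.47; effective n per arm = 500 / 2.47 = 202.4
- p = 41%: 28.7% v 23.8%, SD 0.370, noncentrality 1.34, power about 24%
- p = 60%: 42.0% v 34.8%, SD 0.391, noncentrality 1.85, power about 42%

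By the normal approximation, the chance that this estimate has the wrong sign is about 9% at p = 41% and 3% at p = 60%.

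**The case against.** The conditional definition is the same in the Trial Summary, section 3.4.1 and Table 2, matches the feasibility measure and is what the trial is powered on. Prevention is not ignored, because section 5.9.3 plans a competing-risk analysis of time to first delirium and reports the proportion with delirium. Many cases cannot be prevented by the unit: if the 41% includes the 23%, 23/41 = 56% were delirious on arrival. A delayed or shorter episode still lowers the primary outcome. All of this stands and limits the point, but none of it makes the primary comparison one between comparable groups.

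A reader might infer more than the documents support:
- **That the strategy is bound to look worse.** The first row of the table goes the other way; direction depends on a split the protocol does not give.
- **That prevention could cancel the whole 12-point target.** Under a beta distribution with mean 0.70 and SD 0.30, removing the lowest-burden fifth of all cases lifts the mean to about 82.5%. That needs perfect selection, including among patients delirious on arrival. If only later cases can be prevented and share that distribution, removing their lowest fifth gives about 75%; removing the lowest of them up to a fifth of all cases gives about 77%.
- **That the cost-effectiveness ratio certainly omits prevented days.** Sections 6.1 and 6.2 do not say how intervention cost is allocated, and the effect is worded as days although section 3.4.1 defines a proportion among cases. The wording is unresolved, not shown to be wrong.

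**Conclusion.** The point holds as a mismatch between the stated purpose and the primary comparison. The outcome is conditioned on an event that follows randomisation and that the strategy aims to prevent, and full prevention earns no credit. Preventing half of the later cases would cut all-inpatient burden from 28.7% to 21–25% while the primary outcome ends anywhere from 66% to 77%. Those figures rest on the feasibility percentages, the 70% mean, the assumption that nothing else changes, and an assumed range for the split. They show possible size and sign, and are not a forecast.

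The secondary analyses soften the problem but sit outside the primary comparison. Time to first delirium is missing from section 3.4.2, and the proportion with delirium is only summarised. This calls for added analyses and clearer wording. It does not show that the powered primary outcome must be abandoned.

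**What to change.** Keep the conditional primary outcome and its sample size, and make four changes.

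1. Pre-specify a key supportive analysis: the proportion of inpatient days with delirium in all consecutive eligible inpatients whose records are reviewed, scored 0 if delirium-free, with the same two-level model. Report it beside the primary result, with its components by arm: percentage with delirium, delirium days, and length of stay.
2. List time to first delirium and occurrence of delirium in section 3.4.2, and compare occurrence formally between arms.
3. Define the effect in the cost-effectiveness ratio as mean delirium days per admission over all inpatients, and reconcile sections 3.4.2 and 6.2 with section 3.4.1.
4. Reword the primary objective (section 3.2 and Table 2) to match the conditional outcome.

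The supportive analysis should not be able to veto the primary conclusion. With power of about 24–42% and a 3–9% chance of the wrong sign under the full effect without prevention, such a rule would sometimes block a true finding.

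**Cost.** The records are reviewed anyway, so the cost is mainly protocol wording and keeping delirium-free stays in the dataset. Two limits remain. The size of the all-inpatient sample depends on the stop at 30 episodes. The ratio still has length of stay as its denominator: a change from 7 of 10 days to 4 of 5 scores as a rise from 70% to 80%. That is why delirium days and length of stay need separate reporting.
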